Oxidative Stress and COPD. A shift in the antioxidant/free radical balance in favour of free radicals is termed oxidative stress. Superoxide anion (O_2^-) and other free radicals are highly energized molecular species, structurally distinct in that they contain one or more unpaired electrons in their atomic orbital ³³. Although low concentrations of free radicals appear to have important roles in cell signaling, an excess of free radicals can cause a wide spectrum of cellular damage, including lipid peroxidation, alteration of

intracellular redox state, inactivation of enzymes, and damage to DNA. Unsurprisingly, elevated oxidative stress has been observed in smokers³⁴⁻³⁶ and in COPD^{24, 37}. Since the initial observation that O_2^- and other free radicals inactivate nitric oxide³⁸, which plays a fundamental role in regulating endothelial function, it seems logical that the elevated oxidative stress observed in COPD would contribute to endothelial dysfunction. One method to reduce oxidative stress is through a reduction in superoxide anion (O_2^-), which would limit the degradation of NO, thus increasing its bioavailability. Antioxidant supplementation has been utilized as a means to reduce oxygen free radicals and increase NO bioavailability in several clinical populations³⁹⁻⁴¹.

3. Inclusion and Exclusion Criteria

List the inclusion/exclusion criteria:

- Inclusion
 - o 24 patients with medically diagnosed COPD
 - 24 apparently healthy controls
- Exclusion
 - FEV1/FVC >0.7 (normal lung function in patients only)
 - Clinical diagnosis of heart disease or diabetes
 - Vasoactive medications (i.e. nitrates, beta-blockers, Viagra etc.)
 - o uncontrolled high blood pressure
 - high blood pressure in your lungs
 - o thyroid problems
 - o Fluid in the lungs
 - Sleep apnea
 - o Anemia
 - o Raynaud's Phenomenon
 - o GI bleeding
 - Gangrene of the digits
 - History of low platelets or coagulopathies
 - Phenylketonuria (PKU)
 - o Pregnant
 - Lactation
 - Any allergy to Kuvan

4. Number of Subjects/Records/Samples Collected

A maximum of 48 volunteers will be needed for this entire research study. For patients, there are 2 protocols which each consist of 6 visits each. We would like to recruit 12 patients with COPD that will be asked to complete the Kuvan protocol and an additional 12 patients that will be asked to complete the Antioxidant protocol. Apparently healthy controls (n=24) will be asked to only complete visit one.

5. Recruitment Methods

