Patients with COPD will be recruited from the Pulmonary and Critical care medicine unit, family medicine, internal medicine, and local outreach clinics associated with Georgia Regents University. We will also use I2B2 to pull up inclusion and or exclusion criteria for potential participants as well as power chart to gather contact information; for this purpose a Waiver of Consent, Waiver of HIPAA Authorization along with the telephone screening forms that will be used to contact potential participants will be approved by the designated IRB before patient recruitment takes place. The main source of control subject recruitment will be the parents of the subjects enrolled in other studies here at the Georgia Prevention Institute (GPI). The GPI sees approximately 10,000 subject visits per year (both children and adults).

Click here to enter text.

6. Procedures Involved

Body Composition. The subjects body fat, bone, and lean tissue will be measured at the beginning of the study with a low level x-ray machine called dual-energy x-ray absorptiometry (DXA) for short. These tests give the subjects body about 4 extra days worth of the type of background radiation that everyone receives every year from the environment. The subject will be asked to lie still on a table with their eyes closed while a mechanical arm moves above their body measuring their body composition. Body Mass Index (BMI) will also be calculated using measurements of the subject's height and weight. Waist to Hip Ratio (WHR) will be measured using a vinyl tape measuring around their waist and hips.

Pulmonary Function Test. All volunteers will perform a lung function test to measure how well their lungs work. This involves taking a deep breath and then blowing into a tube as hard as they can, until they cannot blow any further. We will also measure how well the air crosses through the lungs by having each participant breathe a mixture of gasses (10% He, 21% O2, 0.3% CO, and balance N2) and having them hold their breath for 10 seconds. Following the baseline lung function test, it is possible that the volunteer will be excluded from the study if their lung function does not meet the criteria above.

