Six-Minute Walk Test: Potential risk related to this test are few but include chest pain, shortness of breath, leg cramps, staggering, sweating, and pale skin color in the face. Every effort will be made to minimize these risks. A staff member who is certified in basic life support will be present at all times. We will have a chair available throughout the test if the patient needs to take a break. Oxygen will also be readily available.

Local Heating: We measure the temperature of the subject's skin under the ring holders. The skin will feel very warm but should not hurt. The heating of the water will make the skin of the subjects arm under the holders red like when taking a hot bath. The redness will not last more than a few hours. Some people may be more sensitive to the heating than others. If the subjects arm feels too hot, the subject has been instructed to tell us, and we will reduce or stop the heating.

Visits Required:

There are six visits required for all COPD subjects for this study, a preliminary visit, and 5 experimental day visits (baseline, 4 weeks, 8 weeks, 12 weeks, and a follow up visit on week 16). Control subjects will need to only complete one experimental day visit.

Subjects may participate in both protocols but they do not have to. If they do wish to participate in both protocols, they must wait at least 4 weeks in between protocols.

Click here to enter text.

7. Data and Specimen Management

a. Describe the data analysis plan, including any statistical procedures: The proposed investigation is an open-label dose response investigation. More importantly, this investigation is a pilot project that is based on the transient findings of previous funded American Heart Association grant. Nonetheless, for the Kuvan protoco we will employ a 3 x 5 (dose x time) mixed factorial ANOVA with the repeated factor being time. For the Antioxidant protocol we will employ a Repeated measures ANOVA For both protocols we will run planned comparisons of the treatment response to the control data to determine the effects of the treatment relative to the baseline value of the control. In an attempt to reduce the family wise error rate, planned comparisons will als be made for the interaction between baseline and 12 weeks for each dose with comparison made with the withdraw period.	our l A. Soo ons	
b. When applicable, provide a power analysis:	□ N/A	
The power and sample sizes could not be determined from the acute intervention study.		

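### Controls have no lung-function limit and no age or sex criterion, matching or adjustment, so comparability of the control benchmark in Section 7a is not assured

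*Combined protocol and SAP*

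**What the plan says.** Section 3 admits "24 patients with medically diagnosed COPD" and "24 apparently healthy controls". Its one lung-function item is the exclusion "FEV1/FVC >0.7 (normal lung function in patients only". Other exclusions, such as "Clinical diagnosis of heart disease or diabetes" and "Vasoactive medications (i.e. nitrates, beta-blockers, Viagra etc", are not limited to patients and so apply to controls as written. No age range, sex requirement or matching rule is given for either group.

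Section 5 recruits patients from pulmonary, family and internal medicine and outreach clinics. For controls: "The main source of control subject recruitment will be the parents of the subjects enrolled in other studies" at the institute.

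Section 6 (Pulmonary Function Test) has all volunteers tested and adds that "it is possible that the volunteer will be excluded from the study if their lung function does not meet the criteria above".

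Section 7a plans, for both protocols, comparisons of the treatment response with the control data "to determine the effects of the treatment relative to the baseline value of the control". It names no outcome and no covariate. Section 7b gives no power analysis.

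**The concern.** The controls are the only untreated group. All three Kuvan groups receive active drug, the antioxidant protocol is analysed as a single group over time, and the study is open-label. Controls make up half of planned enrolment (24 of 48), and their single baseline value is the outside reference for both protocols.

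Two things could move that reference for reasons unrelated to COPD or treatment. First, a control with airflow obstruction breaks no written rule. Section 2 itself reports that FMD impairment in COPD seems to go with the degree of obstruction, so such a control may carry the abnormality under study and pull the benchmark towards the patients. Second, the two groups come from different sources and nothing makes them alike in age or sex. If the vascular outcomes depend on either, part of any patient-control difference would reflect recruitment rather than disease. At stake is the reading of any statement that patients start below the control level or approach it on treatment.

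**Working it through.** **Step 1: does the lung-function provision bind controls?** Section 6 refers back to the eligibility criteria. Section 3 contains one ratio criterion. It removes patients whose ratio is above 0.7 and is limited to patients. For controls the reference finds no limit. A control with a ratio of 0.60 would meet every written criterion, provided the investigator still judged that person apparently healthy.

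**Step 2: is the test available?** Section 6 lists pulmonary function testing on both the preliminary day and the experimental days. Controls are therefore due to have it whether their single visit is visit one (Section 4) or an experimental day (Section 6). The schedule note, however, lets procedures be omitted or moved, and no order relative to the vascular tests is fixed.

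**Step 3: is age or sex dealt with elsewhere?** Sections 3, 5 and 7a were read for an age range, matching or adjustment. None is stated.

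**Step 4: which analyses use controls?** The Kuvan ANOVA has dose (3) and time (5) as factors, and the antioxidant analysis is a repeated-measures ANOVA. Neither includes controls. Only the planned comparisons with the control baseline are affected. FMD and PWV are presumably the benchmarked outcomes, as vascular tests listed for experimental days, but Section 7a does not say so.

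**Step 5: how large could the effect be?** The plan states no effect size, SD, alpha or power, so there is no figure to reproduce. The following is illustration on assumed inputs: common SD of 1, two-sided alpha of 0.05, normal approximation.

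*Age or sex imbalance.* Let d be a shift in SD units due to imbalance alone. Then SE = √(1/24 + 1/n) and the chance of a nominally significant difference is Φ(d/SE − 1.96) + Φ(−d/SE − 1.96). For n = 12, SE = √(1/24 + 1/12) = 0.354. With d = 0.5, d/SE = 1.414 and the chance is Φ(−0.546) + Φ(−3.374) ≈ 0.293.

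| Controls v patients | SE | d = 0.25 | d = 0.5 | d = 1.0 |
|---|---|---|---|---|
| 24 v 24 (all patients) | 0.289 | 14% | 41% | 93% |
| 24 v 12 (one protocol) | 0.354 | 11% | 29% | 81% |
| 24 v 4 (one Kuvan dose, if 12/3 = 4) | 0.540 | 7.5% | 15% | 46% |

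*Obstructed controls.* Let a fraction q of controls have obstruction and, as a worst case, fully patient-like vascular values. The control mean is then (1 − q) × healthy + q × patient, so a share (1 − q) of the true difference remains. The expected number is 24q and the chance of at least one is 1 − (1 − q)^24. The last column assumes a true difference of 1 SD at 24 v 12.

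| q | Expected of 24 | Chance of at least one | Difference retained | Power |
|---|---|---|---|---|
| 0 | 0 | 0% | 100% | 81% |
| 0.05 | 1.2 | 71% | 95% | 77% |
| 0.10 | 2.4 | 92% | 90% | 72% |
| 0.20 | 4.8 | 99.5% | 80% | 62% |

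On these inputs a group imbalance does more harm than a few obstructed controls. None of the values of d or q comes from the documents.

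**The case against.** The strongest reply is that this is a drafting gap. Controls must be apparently healthy, several cardiometabolic and respiratory exclusions apply to them, and the Section 6 provision speaks of any volunteer. The restriction to patients has an obvious purpose, since an unrestricted exclusion above 0.7 would remove every normal control. This largely stands as an account of intent. It does not supply a cut-off, so exclusion of a control would be a matter of judgement, possibly made after the vascular results are known. It also does not touch age or sex.

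A reader might infer four stronger things, and the documents support none of them:

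- **That the control value is not a valid healthy value.** The documents contain no age or lung-function data on controls. They show that comparability is unsecured, not that the value is wrong.
- **That the controls are younger than the patients.** Being a parent of a participant fixes no age. The institute sees adults as well as children, parents are the main but not the only source, and no ages are given for either group.
- **That the two problems cannot be separated afterwards, making the comparison uninterpretable.** Spirometry would identify an obstructed control, and age and sex can be entered in the analysis. The defect is that no such step is planned.
- **That the main analyses are compromised.** The dose-by-time and repeated-measures ANOVAs use patients only.

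It is also fair to say that matching on age and sex does not make the groups alike in smoking, which Section 2 links to oxidative stress. The remedy improves comparability without completing it.

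**Conclusion.** The point holds as a gap in the control comparison. As written, Section 7a gives an unadjusted comparison of two differently sourced groups, and the lung-function provision has nothing to apply to controls. The age and sex part is the weightier. The lung-function part is smaller, but Section 2's own rationale makes it relevant.

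Neither the direction nor the size of any bias can be derived from the documents. Obstruction among controls would tend to shrink the patient-control difference, while an age or sex imbalance could act either way. The percentages above rest wholly on assumed shifts, an assumed SD of 1 and, for obstruction, an assumed fully patient-like vascular response. That FMD and PWV are the benchmarked outcomes is also an inference. This should be corrected before controls are enrolled, because matching is not available afterwards. It does not undermine the analyses of patients alone.

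**What to change.** **Section 3:** exclude controls with FEV1/FVC of 0.7 or below on the study spirometry, and apply the rule before their vascular results are seen.

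**Section 7a:** adjust the patient-control comparisons for age and sex, report the age and sex distributions of both groups, and name the outcomes to be benchmarked.

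**Section 5, where feasible:** frequency-match controls to patients on age band and sex.

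**Cost:** a few lines of text and no new procedure, since all volunteers already have spirometry. A few screened controls would be replaced. Control recruitment may be slower if matching means going beyond the parent pool, and the more the pool differs from the patients, the slower it will be. Adjustment costs some precision. At 24 v 12, with one linear term each for age and sex, residual degrees of freedom fall from 36 − 2 = 34 to 32. The larger loss comes if the groups overlap little in age, when adjustment leans on the model. That is the reason to match where possible and not to rely on adjustment alone.

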Protocol Title: Long Term Nitric Oxide Bioavailability on Vascular Health in Chronic Obstructive Pulmonary Disease (COPD-LT)

Principal Investigator: [name], CES, FACSM

1. Objectives

Researchers have found a link between chronic obstructive pulmonary disease (COPD) and heart disease; however, a link is all they have found. In a previously funded grant, using a double blind, randomized experimental design, we explored the effect of an acute dose of Kuvan or an antioxidant cocktail (1000mg of vitamin C, 600IU of vitamin E, and 600mg alpha-lipoic acid) on vascular health in patients with COPD. Consequently, we found in separate experiments, that a single dose of both antioxidants and Kuvan transiently improves vascular health in patients with COPD. The current project is an attempt to expand on our previous findings and explore the effects of sub-chronic use of antioxidants and Kuvan on sustaining the improvements in vascular health in COPD.

2. Background

Chronic obstructive pulmonary disease (COPD) affects up to 14 million people and is among the top five leading causes of death worldwide. Although COPD is a disease of the lungs, recent evidence indicates that COPD is associated with multiple systemic consequences including vascular endothelial dysfunction. Recently, it has been suggested that more patients with COPD die from cardiovascular disease and coronary heart disease than of direct pulmonary complications. Examination of the mechanisms that contribute to a reduction nitric oxide (NO) bioavailability resulting in vascular endothelial dysfunction in patients with COPD are important as endothelial dysfunction has been indicated to be an independent predictor of future atherosclerotic cardiovascular disease and events.

NO Bioavailability and Vascular Function. Evidence indicates that a reduction in concentrations of NO, a hallmark of proatherogenic states, facilitates atherosclerosis. The flow-mediated dilation (FMD) technique, which represents a fundamental assay of NO bioavailability, has provided means to evaluate vascular endothelial function noninvasively and has been shown to correlate with invasive testing of coronary artery endothelial function.

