Arterial Function (FMD). This test looks at how artery expands with changes in blood flow and is used to characterize the health of the subject's arteries. The subject will lie on their back for 20 minutes to rest. We will then measure the function of the artery by scanning an artery in the arm. Following baseline measurements, a blood pressure cuff placed around the subjects forearm will be inflated to 250 mm Hg to stop blood flow for 5 minutes. Blood flow and velocity and arterial diameters will be recorded for 2 minutes following the release of the cuff.

Ankle Brachial Index (ABI). This test is done by measuring the blood pressure in both the arm and the lower leg (ankle) while the subject is lying down. We will use this test to screen for peripheral vascular disease.

Six-Minute Walk Test (6MWT). This test measures the distance that a patient can quickly walk on a flat, hard surface in a period of 6 minutes. A line, 30 m in length, will be drawn out in tape with cones at each end of the line to mark the turnaround points.

Skin Blood Flow. The laser imaging camera is a special camera that shines a low energy laser light on the surface of the skin to measure blood flow. The FLPI makes graphs, photos, and movies of skin blood flow. There are no known risks associated with the laser imaging camera. The small skin probes can hurt the eye if you stare into the light for a long time; however, we do not turn on the laser until the probes are taped to a surface of the skin.

Iontophoresis. Acetylcholine, sodium nitropruside and L-NAME are vasoactive substances that will be used to increase and decrease skin blood flow. The amount of drug delivered is based on the amount of current being delivered. Using this technique with such a low level current, there should be no drug that enters the body. Although the current being used is very small (less than 200mA), participants may feel mild skin irritation on the hand or the forearm where the chambers are placed.

Local Heating. We measure the temperature of the skin under the ring holders. The skin will feel very warm but should not hurt. The heating of the water will make the skin of the arm red under the holders like when the subjects takes a hot bath. The redness will not last more than a few hours. Some people may be more sensitive to the heating than others and therefore if the arm gets too hot, we will reduce or stop the heating.

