In this study there will be 5 experimental visits following the preliminary visit each being four weeks apart. For the Kuvan (BH4) protocol, depending on the randomized group the subject is in they will receive either 5 mg, 10 mg, or 20 mg per kg of treatment.

Tentative Schedule of Events:

*Note subject may or may not be asked to perform all procedures during each testing day depending on

time and availability. Also, some preliminary day measures may not be completed on the preliminary day and may be completed some other time during the course of the study.*

Preliminary Day

- Consent
- ABI
- IMT
- DXA Scan
- Pulmonary Function Test
- 6 min Walk Test

Experimental Testing Days

- Continued consent
- PWV
- FMD
- Skin Blood Flow/Local Heating
- Blood Draw
- Pulmonary Function Test

Risk Assessment

All procedures in this study have been routinely performed in research studies in the past and are of low risk to participants.

Venous Blood Draw. Potential risks related with taking a blood sample are few but include slight bruising, pain, a temporary feeling of faintness, and phlebitis. Rarely, there may be a small blood clot or infection at the site of the needle puncture. All blood draws will be performed by a research team member or a nurse who is certified in drawing blood; in either case sterile techniques will be used.

Pulmonary Function Test. There are no known risks associated with this test.

Muscle Function Test. Electrical stimulation of the muscles may be uncomfortable and could be painful. If the muscle stimulation is too painful, we will adjust the stimulation to a level that the subject can tolerate. The study does not require the stimulation to be painful for the study to be successful. Because the stimulator "exercises" the muscle, the muscle may be sore for a few days following the protocol.

Body Composition. The DXA will expose the subject to a minimal amount of radiation. The DXA scan will expose the participants body to about 3 mrem per scan. Everyone receives a small amount of unavoidable background radiation from the natural environment each year. The radiation dose from the DXA scan is equal to less than three to four extra days' worth of natural background radiation. Radiation at significantly higher levels is known to cause cancer; however, the amount of radiation in this study is very low and is not expected to cause bodily injury during the subject's lifetime. The radiation dose discussed

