c. Describe how data and specimens will be handled:	□ N/A	
i. What information will be included in that data or associated with the spe	cimens?	
All specimens will be collected with deidentified information. Specifically, the ID, date, specimen type (i.e. serum or plasma), and analyte to be measured will be included on the tube label.		
ii. Where and how data and/or specimens will be stored?		
Data are stored in subject folders, specimens are stored de-identified in -80 freezers		
iii. How long will the data and/or specimens be stored?		
Until analyzed		

iv.	Who will have access to the data or specimens?
	All investigators who are on the protocol
v .	Who is responsible for receipt or transmission of the data and/or specimens?
	[name]
vi.	How will data and/or specimens be transported?
	According to biosafety procedures

8. Provisions to Monitor the Data to Ensure the Safety of Subjects

This study involves no more than minimal risk study and this section is not required. \Box N/A

The plan might include establishing a data monitoring committee and a plan for reporting data monitoring committee findings to the IRB and the sponsor.

a. Describe the plan to periodically evaluate the data collected regarding both harms and benefits to determine whether subjects remain safe.

Subjects will be monitored the entire time they are in the LIVEP lab. The PI and study team will evaluate the safety for each participant by changes in BP and HR before, during and after treatment.

b. Describe what data are reviewed, including safety data, untoward events, and efficacy data.

During consenting we ask what drugs they are currently taking and we also ask on every visit if there have been any changes to the drugs. We will frequently monitor BP, and HR to determine how the treatment is affecting them.

c. Describe how the safety information will be collected (e.g., with case report forms, at study visits, by telephone calls with participants).

Data is consistently collected during their visits which will monitor how their body is reacting to the drug or cocktail treatment.

d. Describe the frequency of data collection, including when safety data collection starts.

This done with every visit, subjects BP, and HR are consistently monitored during the duration of their visit

e. Describe who will review the data.

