- Quantity Affected
- Detailed Description of complaint
- Study Protocol Number
- Investigator Name

- Site Contact
- Site Number
- Subject Number
- Name and contact information of the person who is reporting the complaint as well as name and contact information of the complainant. The reporter will be contacted by BioMarin Product Complaint Quality Assurance Department.

Investigator or designee (Reporter) will use his or her best efforts to report Complaints to BioMarin within five days of learning of the Complaint.

Investigator or designee will submit the complaint information by email at [contact] or by fax at [contact].

There are no costs for participating in the study; however, the subjects will be responsible	□ N/A
for the costs of transportation to the Georgia Prevention Institute for clinic visits.	
There is no cost for the medications/supplements used during the study or for any of the	
procedures and tests required for this study. The cost of the lab draws during the study will	
be covered by the study investigators	
a. If applicable, describe risks to others who are not subjects.	X N/A

11. Potential Benefits to Subjects

COPD is the 3rd leading cause of death in the US. Participation in this study will advance our knowledge and understanding of the link between heart and lung disease and contribute to the treatment and prevention of COPD. Although there is no direct benefit to the participant, access to the results and information on 1) cholesterol values, 2) skeletal muscle function test, and 3) functional and structural measurements of the health of the participants arteries will be available. They may also choose whether they receive the results of these assessments; however, if the participant choose to receive the results, [name] or another qualified research member will explain the results to the participant in detail.

12. Confidentiality

To minimize the risk of the subject confidentiality, no testing material will be linked to the name, SSN, medical record number, or any other identifiable markers. Instead, each participant will be assigned a random identification number (ID). Those unique ID numbers will be used in the data file. A list of participants' names and their ID numbers is kept in a separate file and only the Principal Investigator and collaborating investigators named on the informed consent document will have access to this file. E-mail addresses and phone numbers are not shared with outside parties.

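### Nothing keeps the person measuring the FMD recordings or saved skin blood flow images unaware of visit or dose, so a reading shift would add directly to within-patient change

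*Combined protocol and SAP*

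**What the plan says.** Section 7a describes the study this way: "The proposed investigation is an open-label dose response investigation". The only blinding language in the document concerns the earlier acute-dose work (Section 1): "In a previously funded grant, using a double blind, randomized experimental design".

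On measurement, the FMD paragraph of Section 6 says "Blood flow and velocity and arterial diameters will be recorded for 2 minutes following the release of the cuff". The skin blood flow paragraph describes a laser camera that produces graphs, photos and movies, so that outcome also leaves saved files. Pulse wave velocity (PWV) is taken with a hand-held device during the visit, and no later reading step is described. Section 6 does not say who measures the FMD recordings, whether software does it, or what that person knows about the patient.

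The coding provisions protect identity. Section 12 gives each participant one random ID, used in the data file. For blood tubes, Section 7c says "the ID, date, specimen type (i.e. serum or plasma), and analyte to be measured will be included on the tube label". It also says that data are kept in a folder per subject and that all investigators on the protocol have access.

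On design, Section 6 says of Kuvan: "depending on the randomized group the subject is in they will receive either 5 mg, 10 mg, or 20 mg per kg of treatment". Section 4 adds: "We would like to recruit 12 patients with COPD that will be asked to complete the Kuvan protocol and an additional 12 patients" for the antioxidant protocol. Under the visits required, "Control subjects will need to only complete one experimental day visit". Section 7a plans a 3 x 5 dose-by-time mixed ANOVA for Kuvan, a repeated measures ANOVA for antioxidants, comparisons with the control data, and comparisons of baseline, week 12 and withdrawal for each dose.

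**The concern.** Treatment can be open-label without the measurement being so. Here the plan leaves both open. Filing by subject places one patient's visits together, and a single ID per participant does not hide visit or dose. The hoped-for direction is also known: Section 1 reports that single doses improved vascular health and says this project asks whether the improvement can be sustained. Someone measuring a week-12 FMD recording may therefore know that a larger dilation is hoped for, and at week 16 that a fall-back would fit the hypothesis.

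A shift in reading that follows the visit is added to the within-patient change. No untreated patient series over the same visits exists to subtract it. The antioxidant time effect and the within-dose Kuvan contrasts are the most exposed. The planned comparisons of treatment response with controls would take in a shift in on-treatment readings too. The study calls itself a pilot, but it plans significance tests, and a spurious change could misdirect later work.

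**Working it through.** The documents state no alpha, SD, effect size, power or reader-error figure, so there is no figure of the plan's own to reproduce. The calculation below is a sensitivity illustration.

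**Inputs from the documents**
- 12 Kuvan and 12 antioxidant patients (Section 4).
- Three randomized Kuvan doses, with no zero-dose arm (Section 6).
- Five experimental visits: baseline and weeks 4, 8, 12 and 16 (Section 6).
- Baseline, week-12 and withdrawal comparisons within each Kuvan dose (Section 7a).

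**Assumptions**
- Two-sided alpha of 0.05 and normally distributed changes.
- Equal allocation, 12 / 3 = 4 per dose; no ratio is stated.
- True effect zero, with a constant reading shift b in units of the SD of within-patient change.
- A paired t-test of baseline against week 12. For the antioxidant group this stands in for the planned repeated measures ANOVA.

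**Within-patient change.** With T noncentral t on n - 1 degrees of freedom and noncentrality b√n, the false-positive rate is P(|T| > t(0.975, n - 1)). The critical values are 3.182 for n = 4 and 2.201 for n = 12.

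| Group | b | b√n | False-positive rate |
|---|---|---|---|
| One Kuvan dose, n = 4 | 0 | 0 | 5.0% |
| | 0.25 | 0.500 | 6.5% |
| | 0.5 | 1.000 | 11.1% |
| | 1.0 | 2.000 | 28.9% |
| Antioxidant, n = 12 | 0 | 0 | 5.0% |
| | 0.25 | 0.866 | 12.4% |
| | 0.5 | 1.732 | 35.3% |
| | 1.0 | 3.464 | 88.3% |

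Simulation with 200,000 runs per case agreed: 11.1% and 29.1% for n = 4, and 35.6% and 88.3% for n = 12, at b = 0.5 and 1.0.

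**Dose comparison.** If every dose carries the same shift, the differences in mean change between doses are zero and the test keeps its 5% rate. For a spurious dose effect the shift must rise with dose. Take shifts of 0, b/2 and b in three groups of 4. The deviations from their mean are -b/2, 0 and b/2, so the noncentrality of the F test on change scores is 4 × (b²/4 + b²/4) = 2b², with 2 and 9 degrees of freedom.

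| b (top dose) | 2b² | False-positive rate |
|---|---|---|
| 0.5 | 0.5 | 7.8% |
| 1.0 | 2.0 | 17.3% |
| 1.5 | 4.5 | 34.3% |
| 2.0 | 8.0 | 56.0% |

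To reach the 35% or so that a shift of 0.5 SD gives in 12 antioxidant patients, the dose comparison needs a graded shift of about 1.5 SD.

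**The case against.** Four objections deserve weight.

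**The randomized doses offer protection.** A reader might infer that every efficacy contrast rests on visits alone and is equally exposed. Section 7a does not support that: dose is a randomized between-patient factor, and a shift shared by all doses cancels there. This stands, and it limits the point to within-patient change.

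**The larger rates are not the Kuvan rates.** The 12% and 35% figures need 12 patients in one paired test. Section 7a plans the Kuvan comparisons within each dose, where the assumed 4 patients give 6.5% and 11%. This stands too.

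**The size of the shift is unknown.** The calculation shows what a shift would do, not that one is likely. If diameters are traced by software, there is less room for discretion. The documents do not say, so the rates are a range under stated assumptions. What stands on the text is that no safeguard is written down.

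**PWV and blood tubes differ.** PWV is acquired live, so coding saved files cannot remove operator influence during acquisition. The tube labels carry ID and date, but nothing shows that the assays leave room for discretion, and relabelling would add a risk of mix-up. Neither supports a request for coded tubes.

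The open-label and pilot status does not answer the point. Neither requires that recordings be measured by someone who knows the visit.

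**Conclusion.** The gap is real. It concerns the measurement of FMD recordings and saved skin blood flow images, and its effect on within-patient change. If a visit-related shift occurred, it would pass undiluted into the antioxidant time effect and the within-dose Kuvan contrasts. Shifts of 0.25 to 0.5 SD of the change would raise a 5% error rate to about 6.5% to 11% in one Kuvan dose group of 4, and to 12% to 35% in the 12 antioxidant patients. The shift sizes, alpha, the test and the 4-per-dose split are all assumptions.

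A reader might go further and conclude that any effect found would be an artefact of reading. The documents do not support that: they give no reader variability and do not describe the measurement method. Nor do they support a claim that the dose comparison is seriously threatened, since that needs a large shift graded by dose. The change is worth making because it is cheap; this is not a fatal flaw.

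**What to change.** Add to the FMD and skin blood flow procedures in Section 6:

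> Recordings are saved under a random file code that shows neither participant ID, protocol, dose nor date. All files, including those of controls, are measured in random order by existing study staff. Values are locked before the code is opened.

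Where staffing allows, the person measuring should not be the one who scanned the patient; otherwise the masking is partial. For PWV, apply the same coding only to any step read or selected from saved waveforms, and state that operator influence during live acquisition remains. Leave the tube labels as they are.

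The cost is one procedure paragraph and a code list to keep. Measurement is done in batches after the visits, so participants who ask for their arterial results (Section 11) would receive them later. Arms, visits, sample size and staff do not change.

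If masked reading removes the shift (b = 0), each test above returns to its 5% rate. Regression to the mean, familiarization and time trends would remain, because there is still no concurrent untreated series.
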